To do so, we will develop a cost utility model in accordance with best practice recommendations for modeling from the ISPOR Good Research Practice Task Force [43] and will follow the guidelines set out by the National Institute For Health and Clinical Excellence Reference Case [44]. We will develop a decision tree cohort Markov Model using TreeAge (TreeAge Software, Inc., Williamston, MA) with methods similar to those previously described by Rosen *et al* in their analysis of the cost effectiveness of resistance testing-based management of virologic failure [23]. The outcome of interest will be the cost per QALY (\$/QALY), presented as an incremental cost-effectiveness ratio. We will populate the model for the first 9 months with comparative efficacy, health-related quality of life (EQ5D questionnaire), and resource allocation data derived directly from the clinical trial. We will value health-related quality of life using the time trade off approach for a reference population in sub-Saharan Africa as adopted in similar HIV-related cost-effectiveness analyses [45]. Thereafter, we will use published data on the natural history of HIV disease to model clinical outcomes every 6 months after study conclusion over a patient's lifetime, including risk of opportunistic infections, hospitalization, quality of life and death [46-50].

We will vary the probability of each outcome by CD4 category, presence (or not) of detectable viral load and presence (or not) of resistance, to extrapolate cost utility (Table 7). To characterize uncertainty in the model, we will conduct a probabilistic sensitivity analysis (PSA), and present data as cost-effectiveness acceptability curves and PSA plots. Convergent validity will be undertaken to compare the model to similarly published models on the cost effectiveness of resistance testing. Whereas results will be immediately relevant for the South African and Ugandan populations, the proposed structure of the model will be designed such that it may be used for adaptation to countries with similar health care contexts. Results will be presented in US dollars to inform foreign stakeholders.

XI. HUMAN SUBJECTS CONSIDERATIONS

A. Study Risks and Discomforts

1. Risk 1: Unintended disclosure of HIV status or other confidential information. The study intends to minimize this risk through a number of protective measures. Participants will be enrolled directly from the HIV clinic and all study procedures will be performed in adjacent study offices. All interactions with study staff will be in the clinic or private rooms. Study sites have performed thousands of study visits in such a manner. If we visit participants at home to perform tracking of those lost from study, we will make every effort to plan the visit with the participant in advance (e.g. by cell phone), so he or she can make any arrangements necessary for maintaining privacy. We will also approach the home in an unmarked vehicle or on foot to avoid raising concerns. Study forms with identifiers (consent form and tracking form) will be kept in locked file cabinets, which are stored in locked research offices. To maintain data

confidentiality, participants will be assigned a unique identifier on study enrollment, and all study data will be entered on encrypted, password protected study tablets. The tablets will immediately sync study data to an encrypted, password protected Redcap Study Database, and only key study personnel will have access to the database.

2. Risk 2: Discomfort or complication from phlebotomy procedures. Participants will undergo phlebotomy at each study visit. A trained phlebotomist will perform all blood collection using standard precautions. No more than 15 cc (approximately 3 teaspoons) of blood will be drawn on a single day, and no more than 50 cc over the course of the study period.

3. Risk 3: Time Commitments, Transportation costs and other indirect costs of additional study visits. We will reimburse participants for the cost of transportation to study visits performed outside of standard clinical visits. We will also attempt to schedule study visits on the dates of previously scheduled clinical visits to minimize the burden of study procedures. We have attempted to minimize additional time required for study procedures. The longest study visit will be the enrollment visit, largely due to the informed consent procedures, which we estimate will take approximately 1 hour to complete, based on prior similar studies. Study questionnaires will take approximately 30 minutes to complete at the enrollment (Visit 1) and final (Visit 3) study visits.

B. Potential Benefits

1. Potential Benefits to Participants. Study participants will receive nominal incentives for completing the enrollment study visit (e.g. a meal, bar of soap and/or 1 kilogram pack of sugar, depending on the study site). They will also receive study incentives and/or transportation allocation consistent with local expectations, following the established standards with institutional review approval in each country. Details of these reimbursements are described in consent forms. All viral load and resistance testing performed as part of the study will be free for study participants – covered either as part of standard clinical care (as is done for viral load testing in South Africa), or if not, by the study itself. Study participants might benefit from additional viral load and resistance testing results performed as part of the study, or the input from study clinicians trained in management of virologic failure as part of the study protocol. All ART regimens and any other treatments or care will be provided by the partner HIV clinics. Finally, participants might also benefit from knowing that they are helping to improve our understanding of optimal management of virologic failure in sub-Saharan Africa.

2. Potential Benefits to Society and Others. In Uganda, where viral load testing is not always available, the study will provide additional viral load testing free of charge to the study clinics to enhance screening of potential participants, and non-participants might benefit from this service. Results of the study might be of benefit to HIV infected people in the sub-Saharan African region. Over 10 million people in sub-Saharan Africa have accessed ART over the past decade. Approximately 1 in 3 of them who remain on therapy will suffer virologic failure within two years of treatment initiation. Thus, understanding the optimal and most-cost effective method of virologic failure management will have a critical impact on both patients and treatment programs as viral load testing becomes more affordable and available in the region.

XII. REFERENCES

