The study design is an open-label, randomized controlled trial. The study will be conducted at study sites in Uganda and South Africa. The study population will include HIV-infected patients on first-line antiretroviral therapy with a recent viral load >1,000 copies/milliliter (mL). Eligible participants will be randomized to the WHO-based standard of care for management of virologic failure or immediate resistance testing with use of results to guide ART regimen decisions. The study will add the use of a diagnostic test, HIV-1 RNA resistance testing to clinical management of participants in the resistance testing arm, but all other clinical care including provision of ART therapy will be done by clinic sites in keeping with local HIV guidelines. The primary outcome of interest will be viral suppression (<200 copies/mL) at 9 months after study enrollment, and will be assessed using an intention to treat analysis, where missing or absent results will be considered failures. Secondary outcomes of interest will be viral suppression below the limit of assay detection, viral suppression on continuation of first-line (non-nucleoside reverse transcriptase inhibitor [NNRTI]-based) therapy, drug resistance at study conclusion, and mortality, among others. We will analyze primary data collected during the trial to conduct an economic analysis with the goal of estimating the cost-effectiveness of resistance testing versus standard of care.

B. Study Sites

1. Uganda

The Immune Suppression Syndrome (ISS) clinic at the Mbarara Regional Referral Hospital (MRRH) and its partner clinic across the street, the **Mbarara Municipal Clinic**, are PEPFAR-supported clinics, which, in combination, follow more than 20,000 patients with HIV/AIDS and have an established clinical research infrastructure. The clinics employ over 50 clinical care staff including nurses, clinicians, pharmacists, counselors, phlebotomists, patient trackers, and administrative staff. The clinics serve as the primary research sites for the MGH-MUST Global Health Collaborative, which employs an additional 60 research staff with expertise in recruitment, enrollment, participant monitoring, informed consent, data collection, phlebotomy, and laboratory storage and testing.

2. South Africa

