To identify adverse events: (1) study clinicians will perform a clinical review at each study visit and (2) study staff will instruct participants to report any unexpected or severe adverse events to their assigned research assistant. Such a report will immediately be brought to the attention of study principal investigators. Any adverse events that are unanticipated (i.e. not related to standard HIV clinical care or thought to be directly related to study procedures) or severe (e.g. death) will be brought to the attention

[figure not shown]
of the principal Investigator and reported to participating ethical review committees within 7 days. The relevant committee will determine whether it is appropriate to pause the study or alter the study protocol, and will provide suggestions/modifications to the study procedures as necessary. Possible modifications include adding adverse events to the consent form and re-consenting all study participants. The site principal investigator will be responsible for monitoring participant safety at each site on a monthly basis at regularly scheduled research meetings. They will keep a written log of all events and ensure that the ethical review committee is contacted when necessary. They will also keep a log of the outcome of committee decisions regarding adverse events and apprise the research team of any changes that need to occur as a result of such decisions.

X. STATISTICAL CONSIDERATIONS AND ANALYSES

A. Sample Size

We propose to enroll and maintain a sample size of 840 patients, with approximately 420 randomized to each arm. This sample will enable adequate power to detect a clinically significant, 10% or greater rate of our primary outcome (viral load <200 copies/mL) at study conclusion in the RT arm (see below for power calculation). We have selected this threshold because we predict that a finding of this magnitude would be necessary to advocate for a change in current practice of virologic failure management.

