To assess our sample size calculation, we first estimated predicted rates of viral suppression in the SOC arm (Figure 3). To do so, we combined estimated suppression rates for those who remain on first line therapy and those who are switched to second line therapy, due to a persistent elevation in viral load >1,000 copies/mL. Multiple studies have reported that approximately 40% of people (range 27% - 59%) with an initial detectable viral load on first-line therapy load will re-suppress while remaining on first line therapy in the interim [2, 8-10]. Among those who do remain on first-line therapy, we estimate that only approximately 50% will remain suppressed on first-line therapy, owing to both high rates of underlying resistance [8], and sub-optimal adherence. Among patients in the SOC arm with persistent virologic failure on repeat testing who are switched to second line therapy, we expect approximately 80% will re-suppress [35]. In summary, we predict that net re-suppression rates in the standard of care arm compiling those who remain on first-line therapy (20%) and those who switch to second line therapy (48%), will be approximately 68%. While comparative rates of re-suppression with resistance testing are unknown, we hypothesize that resistance testing has the potential to significantly improve viral suppression rates, particularly because rates of resistance at first-line failure are common in the region (65-90%) [7, 8, 36], and because those who are switched to a protease inhibitor-based combination regimen are highly likely to re-suppress [37-39].

Figure 3. Schema of estimated outcomes for participants in the standard of care arm.

Assuming a 68% viral suppression rate in the SOC arm, using a two-sample test of binomial proportions with a Type I error rate of 5%, and allowing for a 5% rate of invalid tests, we compute a 69%, 88%, and 97% power to detect a difference in suppression rates of 8, 10, and 12%, respectively (Table 3). Based on these estimates, we plan to enroll approximately 840 total participants into the study to allow sufficient power to detect a programmatically meaningful 10% superiority rate of viral suppression in the RT arm.

Table 3. Sample Size Estimates

Viral Suppression Rate in SOC Arm	Viral Suppression Rate in RT Arm	Difference in Outcome Rate	α	Sample Size (per group)	Invalid Test Rate	Power
68%	76%	8%	0.05	420	5%	0.69
68%	78%	10%	0.05	420	5%	0.88
68%	80%	12%	0.05	420	5%	0.97

B. Efficacy Analyses

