1. Primary Outcome of Interest

Proportion of patients with a laboratory confirmed suppressed viral load, as defined by <200 copies/mL, at study conclusion (Visit 3).

2. Rationale for Primary Outcome of Interest

We have chosen this as our primary outcome to ensure a balanced outcome assessment 9 months after study initiation, standardization of viral load results across sites with different viral load testing platforms, and because it is an accepted international standard for other international studies of virologic suppression [39, 40].

3. Secondary Outcomes of Interest

- a. Proportion of patients with an undetectable viral load (below limit of detection) at study conclusion
- b. Proportion of patients with an undetectable viral load on first-line (NNRTI-based) therapy at study conclusion
- c. Proportion of patients with International AIDS Society-defined drug resistance mutations to their current regimen ^[41]. As part of this analysis, we will also evaluate for minority drug resistance.
- d. Total patient care costs, including diagnostic testing and ART costs for the study duration
- e. Retention in HIV clinical care at study completion
- f. 9-month mortality rate
- g. Change in health-related quality of life from baseline to 9 months

4. Efficacy Analysis Plan

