Study data coordinators will perform routine reviews of data quality to identify unusual values and missing data entries. Initial analyses will include common exploratory data analyses, table construction, and scatterplots to assist in data quality control, randomization balance, and exploring for possible outliers or leverage points. For our analysis of the primary outcome, we will use a two-sample test of binomial proportions to compare the proportions of participants in each arm who achieve virologic suppression at the study conclusion. For our primary analysis we will conduct an intention to treat analysis. For this analysis, any study participant without a confirmed viral load result at the 9-month study endpoint will be considered as having a detectable viral load (failure). In secondary analyses, we will conduct as-treated analyses for any study participants who do not complete resistance testing in the RT arm or participant who do receive resistance testing in the SOC arm, as documented by clinic records. We will also conduct a sensitivity analysis by censoring participants who are lost-to-follow-up during study procedures and do not have a recorded viral load at study conclusion. The unadjusted comparison of outcome rates will be followed by adjusted comparisons via logistic regression, adjusting for other confounding factors that may explain any heterogeneity or possibly confound assigned treatment and outcome, despite treatment randomization.

The primary analyses will be followed by similar statistical analyses of secondary endpoints including the proportions suppressed on first-line therapy, rates of resistance, rates of retention in care, and the 9-month mortality rate. We will compare health related quality of life measures within participants between baseline and study conclusion using paired t-tests.

C. Economic Analyses

1. Budget Impact Analysis

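### The sample-size table does not say how the 5% invalid tests enter, and its power figures are reproduced by dropping those participants, whom the primary analysis counts as failures

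*Combined protocol and SAP*

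**What the plan says.** **Power.** Section X.A (Sample Size) assumes 68% suppression under standard of care (SOC), 420 per arm and a two-sample test of binomial proportions with 5% type I error. It continues: "allowing for a 5% rate of invalid tests, we compute a 69%, 88%, and 97% power". Table 3 of that section (Sample Size Estimates) prints 68% against 76%, 78% and 80%, with 420 per group and a column giving an invalid test rate of 5%. Neither the text nor the table says how the 5% is used.

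**Origin of the 68%.** It is a sum over two branches, "compiling those who remain on first-line therapy (20%) and those who switch to second line therapy (48%), will be approximately 68" per cent. Neither branch is for a participant without a result.

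**Primary analysis.** Section X.B.4 uses the same test and states that "any study participant without a confirmed viral load result at the 9-month study endpoint will be considered as having a detectable viral load (failure"). Section IV.A agrees: "where missing or absent results will be considered failures". Leaving participants out appears only as a "sensitivity analysis by censoring participants who are lost-to-follow-up during study procedures and do not have a recorded viral load at study conclusion".

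**Target difference.** Section X.A words it in two ways: "This sample will enable adequate power to detect a clinically significant, 10% or greater rate of our primary outcome", and later "power to detect a difference in suppression rates of 8, 10, and 12%, respectively".

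**The concern.** The sample-size calculation and the primary analysis name the same test, so a reader takes the table as the power of the primary analysis. An allowance for invalid tests can work in two ways. Removing participants shrinks the sample and leaves the rates alone. Scoring them as failures keeps the sample, lowers both rates and, if missingness is equal in the arms and unrelated to suppression, also narrows the difference. The printed rates are unreduced and the printed power fits the first way, whereas the plan specifies the second.

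At stake is the claim of adequate power for a 10-point difference, which rests on this table. It is also the figure that would be cited when a null or borderline result is interpreted.

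**Working it through.** **Inputs.** From section X.A: SOC rate 0.40 × 0.50 + 0.60 × 0.80 = 0.20 + 0.48 = 0.68; resistance-testing (RT) rates 0.76, 0.78 and 0.80; 420 per arm; α = 0.05; 5% invalid tests. Sidedness and continuity correction are not stated. Two-sided is used because one-sided does not reproduce the table (399 per arm, uncorrected: 80.9/93.9/98.8%).

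**Formula.** With d = p2 − p1 and p̄ = (p1 + p2)/2:

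- s0 = √(2p̄(1 − p̄)/n)
- s1 = √((p1(1 − p1) + p2(1 − p2))/n)
- power = Φ((d − c − 1.96·s0)/s1), where c = 0 uncorrected and c = 1/n continuity-corrected

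**Step 1: reproduce the stated 69/88/97%.** Take n = 420/1.05 = 400 and leave the rates unreduced. For 0.68 v 0.78, s0 = 0.03139 and s1 = 0.03119. The corrected power is Φ((0.10 − 0.0025 − 1.96 × 0.03139)/0.03119) = Φ(1.153) = 87.6%.

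| How the 5% is used | n per arm | 8 points | 10 points | 12 points |
|---|---|---|---|---|
| Stated in the table | 420 | 69 | 88 | 97 |
| Removed, 420/1.05, corrected | 400 | 68.5 | 87.6 | 96.8 |
| Removed, 420/1.05, uncorrected | 400 | 71.3 | 89.1 | 97.3 |
| Removed, 0.95 × 420, corrected | 399 | 68.4 | 87.5 | 96.7 |
| Flat 5 points off both arms (63% v 71/73/75%), uncorrected | 420 | 69.4 | 87.6 | 96.5 |

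The second and last rows round to all three stated figures. The 399 row just misses two of them: unrounded, 68.43% and 87.47%. The flat deduction keeps the full 10-point gap. If the printed rates are among participants with a result, it requires every invalid test to come from a suppressed participant.

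**Step 2: power of the specified analysis, n = 420, missing scored as failure.**

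*Reading A: the printed rates are among participants with a result.* Assume 5% missing in both arms, unrelated to suppression. The rates become 0.95 × 0.68 = 0.646 against 0.95 × 0.76 = 0.722, 0.95 × 0.78 = 0.741 and 0.95 × 0.80 = 0.760. The 10-point gap becomes 9.5 points. For that row s0 = 0.03181 and s1 = 0.03165, and the corrected power is Φ((0.095 − 0.00238 − 1.96 × 0.03181)/0.03165) = Φ(0.956) = 83.1%. Exact enumeration of the corrected test also gives about 83%.

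*Reading B: the printed rates already count missing as failure.* The 5% then has no role and the rates stand. For the 10-point row the corrected power is Φ(1.234) = 89.1%.

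*Reading C: SOC falls to 64.6%, but the full 8, 10 and 12 points apply to the primary outcome.* With missingness as in A, the 10 points then need 0.10/0.95 = 10.5 points among participants with a result.

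| Reading | Corrected, 8/10/12 points | Uncorrected, 8/10/12 points |
|---|---|---|
| A | 63.2 / 83.1 / 94.4 | 65.9 / 84.9 / 95.2 |
| B | 70.8 / 89.1 / 97.4 | 73.4 / 90.5 / 97.8 |
| C | 67.9 / 86.9 / 96.4 | 70.5 / 88.4 / 96.9 |

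**Step 3: like for like.** Moving from removal to reading A lowers 10-point power from 87.6% to 83.1% corrected, or from 89.1% to 84.9% uncorrected. The fall of 4 to 5 points therefore comes from the handling of missing results, not from a change of formula.

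**The case against.** The strongest reply is that nothing is miscalculated. The 88% can be reproduced, and the plan's wording leans towards the outcome scale. Section X.A sets the target as 10% in the primary outcome, the table's own column is headed as a difference in outcome rate, and section X.B.1 defines that outcome as "Proportion of patients with a laboratory confirmed suppressed viral load", which a participant without a result cannot meet. On that scale 10-point power is 87% to 91% (readings B and C), and the stated 88% lies inside the range.

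Three further points are fair. The flat deduction fits the table without removing anybody, so the fit to removal is not proof. The continuity correction is inferred, since the plan names only a test of two proportions. The 40%, 50% and 80% inputs come from cited studies whose denominators cannot be checked from the plan, so the lack of a missing-result branch does not settle what the 68% means.

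All of this stands, and it limits the point. A reader might infer that the true power is 83% and that 88% is an arithmetic error. The documents do not support that, because 83% holds only on reading A with the stated assumption. What the reply does not remove is that the plan leaves the choice open, and that the derivation closest to hand describes an analysis with participants removed.

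**Conclusion.** The point holds as a modest correction. The role of the 5% is unstated. On the most natural derivation, the printed power belongs to an analysis that drops participants without a result, which is not the specified primary analysis.

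For the specified analysis, 10-point power is 83%, 87% or 89% corrected (85%, 88% or 91% uncorrected), depending on the scale of the rates. The 8-point row varies more, from 63% to 71% corrected against a stated 69%. Readings A and C assume equal missingness in the arms, unrelated to suppression.

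A reader might also infer that the trial is underpowered. It is not on these figures: at the plan's own 5%, power for 10 points exceeds 80% on every reading. One limit remains. The 5% names invalid tests only, whereas participants lost to follow-up or dead without a result are also scored as failures, and section X.A gives no rate for them.

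**What to change.** Restate Table 3 of section X.A for the missing-as-failure primary analysis at 420 per arm, with one named formula (sidedness and continuity correction included). Add a sentence saying whether 68% and 76/78/80% are rates among participants with a result or already count missing as failure, and how the 5% enters. The entries for 8/10/12 points would be:

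- **Rates among participants with a result:** 63/83/94% corrected (66/85/95% uncorrected), with equal missingness unrelated to suppression stated as an assumption.
- **Rates that already count missing as failure:** 71/89/97% corrected (73/91/98% uncorrected), with the 5% column deleted.
- **SOC lowered to 64.6%, full difference on the primary outcome:** 68/87/96% corrected (71/88/97% uncorrected), with the same missingness assumption.

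Add that the 5% covers invalid tests only, while loss and death without a result also count as failures.

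The cost is a few sentences and one table. Section VII records that enrollment is complete; neither enrollment, data collection nor the analysis needs to change. On the first reading the stated power becomes somewhat less favourable.
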